# If preceding variable = "Yes" then impute missing data with "Used successfully".

Data file, identifier patient display id full & autom SVTYP	Notes	Variable name	Variable label	Variable level	Nominal values
general assessments (see Analysis Set and Data Selection)	case listing for QSCNNAS = No OR QSCNNPRB = Yes	COCNNAS	NEW: Connectivity: Please specify reason for unsuccessful use	text	...
	case listing for PRDEXPAS = No OR QSDEXPPR = Yes	CODEXPAS	NEW: Data export: Please specify reason for unsuccessful use	text	...
	case listing for DUOTH = Yes	COOTH	NEW: Data export: Please specify Other	text	...

Used Programmer Features: Printing

Data file, identifier patient display id full & autom SVTYP	Notes	Variable name	Variable label	Variable level	Nominal values
general assessments (see Analysis Set and Data Selection)	decriptive	PRPRNT	Was printing performed	nominal	o Yes o No
		DULAN02	NEW: Printing LAN	nominal	o Yes o No
		DUWLAN02	NEW: Printing WLAN	nominal	o Yes o No
		DUUSB02	NEW: Printing USB	nominal	o Yes o No
		QSPRNTAS	Was printing successful		o Yes o No
		QSPRNTPR #	NEW: Printing: Did you notice any problem* (see definition above)	nominal	o Yes o No problem detected
		DUPRNTTY	Please specify which printer type was used	nominal	...

# If preceding variable = "Yes" then impute missing data with "Used successfully".

Data file, identifier patient display id full & autom SVTYP	Notes	Variable name	Variable label	Variable level	Nominal values
general assessments (see Analysis Set and Data Selection)	case listing for QSPRNTAS = No OR QSPRNTPR = Yes	CODEXPAS	NEW: Printing: Please specify reason for unsuccessful use	text	...

Used Programmer Features: Battery

Data file, identifier patient display id full & autom SVTYP	Notes	Variable name	Variable label	Variable level	Nominal values
general assessments (see Analysis Set and Data Selection)	descriptive with "not used" handled as missing	PRPRGB	Was the programmer used with the battery as power supply (without power cable, usage is optional)	nominal	o used successfully o used, but not successfully o not used
	descriptive, if PRPRGB = "successfully used" then impute missing QSPRGBPR with "No problem detected".#	QSPRGBPR	NEW: battery: Did you notice any problem* (see definition above)	nominal	o Yes, with Adverse Event o Yes, without Adverse Event o No problem detected

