4 INVESTIGATIONAL DEVICE

4.1 Summary description of the device and its intended purpose

The investigational devices used in this clinical investigation are the programmer device Renamic Neo, the programmer software NEO 2001.A and the PK-222-L ECG cable. In the following text the term 'Renamic Neo system' refers to the Renamic Neo hardware, software and the PK-222-L cable, unless otherwise stated.

Renamic Neo is a portable programmer and monitoring device that must enable the intended use of the compatible active implants. It is operated via a touch sensitive display and interrogation of the implant is achieved through a programming head (PGH) or via wandless RF telemetry. This is state-of-the art for cardiac rhythm management (CRM) programmers. Renamic Neo has an integrated PSA, which is used during implantation of BIOTRONIK implantable devices to perform intraoperative tests at the leads. In daily operation, the Renamic Neo can be operated with a power supply brick or, alternatively, with a battery. It can be custom-equipped with a mobile internet stick authorized by BIOTRONIK.

Notable enhancements to Renamic Neo with respect to the predecessor programmer Renamic include:

- Connectivity to fast mobile networks, WLAN, LAN
- Capacitive touchscreen
- High resolution display
- Smaller and lighter hardware compared to the predecessor Renamic
- Operation for a minimum of 1.5 hours through an optional internal battery
- Integration of the Pacing System Analyzer

Unlike Renamic, Renamic Neo does not have an internal printer and instead printing is possible through connection via LAN, USB or wirelessly to an external printer. Apart from the internal printer, all fundamental functionalities of Renamic are also realized in Renamic Neo.

The programmer software NEO 2001.A is highly similar in functioning to the programmer software of the predecessor Renamic. Some software features have been optimized to deliver the same overall PSA functionality and clinical performance, but with improved adaptation of usability to the preferences of the clinical user.

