### **1.2. General information**

The text contains verbatim excerpts from the CIP. Such excerpts are italicized with grey background; e.g.

....

The main aspects and the design of the clinical investigation are presented in chapters 1-4.

General statistical procedures are summarized in chapter 5. Those methods are used in case there is no other specification within this document.

Definitions of the specific dates, e.g. enrollment and termination are presented in chapter 6.

Specific analysis sets are defined in chapter 7.

Descriptive and inferential statistical analyses are handled in following chapters.

Thereby the following statistical considerations are specified:

- Definition of the analysis set for the following analyses, e.g. excluding patients without any measured or imputed data for this endpoint.
- Definition of the endpoint(s) to be analyzed including references to the source data, e.g. CRF sheet and item.
- Treatment of missing and spurious data for evaluation of the above endpoint(s).
- Exclusion of particular information from the evaluation of the above endpoint(s) in addition to the exclusion of patients from the analysis set.
- Descriptive analyses including tables and figures
- Statistical alternative hypothesis/hypotheses (HA) to analyze the above endpoint(s) if available.
- Statistical tests intended to analyze the above hypothesis/hypotheses if available.

All variables are defined in tables using the following columns:

- **Data file** Name of a data file exported from the CDMS with one data row per unique identifier (e.g. patient-specific "patient display ID full" or event-specific record ID); additionally, a new data file ("data SAR") might be generated by merging all relevant data from the original CDMS data files and generating derived variables (e.g. BMI from weight and height or date of first AE episode)
- **Notes** Information whether data has to be presented with "descriptive" methods as defined in the following sub-chapter, data for "case listings" of original data for each patient specified, or "no report" for data needed for generating of derived variables only
- **Variable name** Original name of a variable in the CDMS data file or name of a derived variables (indicated with a suffix " SAR");
- **Variable label** Original labels from the CDMS data will be used for generating the SAR unless a new label is defined in this document ("NEW"); labels might be omitted or shortened ("...") if remaining clear

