	case listing for QSPSAPAS = Somewhat difficult OR QSPSAPAS = Very difficult including programmer serial number DIPRGSNR (see chapter15.1)	COPSAPAS	NEW: Printing: Please specify Somewhat difficult / Very difficult	text	...
	case listing for QSPGPV = No including programmer serial number DIPRGSNR (see chapter15.1)	COPGPV	NEW: Battery: Please specify in case of NO	text	...
	case listing for QSRGPSA = No including programmer serial number DIPRGSNR (see chapter15.1)	CORGPSA	Please specify in case of NO	text	...
	Case listing for all non-missing data including programmer serial number DIPRGSNR (see chapter15.1)	general comment	General comment	text	...

Data file, identifier patient display id full	Notes	Variable name	Variable label	Variable level	Nominal values
data SAR	case listing for any reported problem: QSPGHPRB, QSRFTPRB, QSSAPRB, QSPRPRB, QSPITPRB, QSDFFPRB, QSPRGPRB, QSDFTPRB contain "Yes"; DUPSAAS = No, QSCNNPRB, QSDEXPPR, QSPRNTPR, QSPRGBPR QSANYPRB contain "Yes"	DIPRGSNR (see chapter 15.1)	Programmer serial number	text	...

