### **13.4. Hypotheses & Statistical Tests**

There are no pre-defined statistical hypotheses.

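### SAP chapter 13: the printing-failure listing outputs the data-export comment, three usability comments carry another function's label, and one listing names an undefined variable

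*SAP*

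**What the plan says.** Each block of SAP chapter 13 has a table of items for frequency reporting and a case listing that prints a free-text comment when an item signals a failure.

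- *Data export*: the listing is "case listing for PRDEXPAS = No OR QSDEXPPR = Yes". It outputs CODEXPAS with the label "NEW: Data export: Please specify reason for unsuccessful use".
- *Printing*: the listing is "case listing for QSPRNTAS = No OR QSPRNTPR = Yes". It also outputs CODEXPAS, now with the label "NEW: Printing: Please specify reason for unsuccessful use".
- *Assessment of Programmer Features*: COPSAPAS, the comment on whether PSA parameters are easy to find, has the label "NEW: Printing: Please specify Somewhat difficult / Very difficult". COCNSAS and COPGPV, which belong to two connectivity-settings items, are labelled as data export and battery.
- The last table of that block lists programmer serial numbers for any reported problem and includes QSDFFPRB among its triggers.

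SAP 1.2 makes the labels operative: "Original labels from the CDMS data will be used for generating the SAR unless a new label is defined in this document". SAP 14.1 repeats chapter 13 for PHD and follow-up. SAP 13.4 states: "There are no pre-defined statistical hypotheses".

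**The concern.** The study is descriptive throughout. Protocol 7.2.1 sets no hypothesis and Protocol 11.5 sets no pass/fail criterion, so the tables and listings are what the report will contain on performance and usability. A listing with the wrong comment or the wrong heading is therefore an error in the product itself.

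The slips also fall on features the protocol singles out. Protocol 4.1 says "Unlike Renamic, Renamic Neo does not have an internal printer", so printing now depends on an external printer. Protocol 4.7.1 describes PSA software changes, Protocol 8.1.3 focuses the performance measurements on features new since the predecessor, and Protocol 7.5 names PSA assessment and printing as data of interest. A reader of the report could take a complaint about PSA parameters for a complaint about printing, or find no usable reason beside a failed print.

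**Working it through.** No arithmetic beyond a count applies. The check sets trigger, output variable, label and item definition side by side for each affected listing.

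**1. Printing comment.** Both listings read the general assessments file, which SAP 5.9 defines with one row per patient and visit type. There is thus one CODEXPAS value per visit, and it is printed as the export reason in one place and the printing reason in the other. Elsewhere in the chapter the comment variable shares the stem of its own item: QSCNNAS/COCNNAS for connectivity, PRDEXPAS/CODEXPAS for export, PRPRGB/COPRGB for battery, QSPGHAS/COPGHAS for programmer-head telemetry. QSPRNTAS has no counterpart anywhere in the SAP. Two cases follow:

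- Separate CRF fields: the printing listing shows whatever was written about export, or a blank if nothing was, under a printing label.
- One shared CRF field: the output may be right, but the SAP gives the same variable two different labels without saying that it is shared.

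**2. Labels.**

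| Comment | Triggering item | Subject of the item | Label in the SAP |
|---|---|---|---|
| COCNSAS | QSCNSAS | finding connectivity settings | Data export |
| COPSAPAS | QSPSAPAS | finding PSA parameters | Printing |
| COPGPV | QSPGPV | range of connectivity settings | Battery |

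Trigger and comment match in all three rows, so the right patients and the right text are selected. Only the label is wrong. The three labels repeat, in order, the three sub-headings just before this block (data export, printing, battery), which points to carried-over text. Under SAP 1.2 these labels replace the database labels in the report.

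**3. Undefined variable.** The LV VectorOpt problem item is QSDFPPRB, both in the item table and in its own case listing under *Used Programmer Features: Implant*. QSDFFPRB appears only in the any-problem listing and is defined nowhere. That listing outputs only the programmer serial number. The VectorOpt listing uses QSDFPPRB, outputs the reason (CODFPAS) and includes the serial number.

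**Count.** 1 output variable + 3 labels + 1 variable name = 5 cells. Chapter 14 works by reference, so correcting chapter 13 corrects both. The chapters cover 50 planned implantations and 100 planned PHD or follow-up cases (Protocol 11.2).

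**The case against.** The strongest case on the other side is that these are editorial slips in supporting listings and that little is lost.

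- *The comment field may be shared.* The CRF is not among the documents, and Protocol 7.5 and Table 3 group printing under data export. This stands as a limit. A reader might infer that every printing failure loses its reason; that holds only if the CRF has a separate printing field. The naming pattern, and the fact that connectivity has its own comment variable, make a slip the likelier explanation but do not prove it.
- *Printing is reported by other routes.* Printing success and problems are tabulated, reported printing problems enter the any-problem listing with the serial number, and general comments are listed in full. A failure may also be a device deficiency under Protocol 18.3. This stands for the occurrence of failures. It stands only partly for the reasons: the device-deficiency listing in SAP 10.2 has no description of the deficiency, and a general comment need not mention printing.
- *The label errors lose no data.* Correct. The comments are printed and the items' frequency tables keep their proper labels. The harm is misattribution of free text.
- *The undefined variable hardly matters.* Largely correct. A reader might infer that VectorOpt problems or their reasons go unreported, but the dedicated listing still shows reasons and serial numbers. A one-letter difference could also be a PDF reading error.

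A careful programmer might notice all of this, but SAP 1.1 offers the document as detailed instructions for the analyses, and as instructions these cells are wrong.

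**Conclusion.** The point holds as a set of specification errors in descriptive case listings, with low severity. Followed literally, chapter 13 and, through it, chapter 14 would put comments on connectivity settings and PSA parameters under other functions' labels. They would also fill the printing listing from the data-export comment. The first effect follows from the SAP text alone. The second assumes that the CRF does not use one shared field for export and printing. The undefined variable affects only the combined serial-number listing.

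The number of affected rows cannot be stated, because the documents give no expected frequency of printing failures or negative usability comments. The documents do not support a reading that the performance assessment as a whole is compromised: the frequency tables in these chapters use the correct items, and the adjudicated ADE/DD endpoints in SAP chapters 10 and 11 use other variables.

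**What to change.** Before CDMS closure, make five cell corrections in SAP chapter 13:

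1. Check the CRF. Replace CODEXPAS in the printing listing with the printing comment variable or, if the CRF has one field for both functions, say so and label it accordingly in both listings. The variable name has to come from the CRF, since the SAP does not contain it.
2. Relabel COCNSAS as connectivity settings.
3. Relabel COPSAPAS as PSA parameters.
4. Relabel COPGPV as range of connectivity settings.
5. Verify QSDFFPRB against the source file and the database export, and correct it to QSDFPPRB.

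Chapter 14 then needs no separate change to these cells. Protocol 11.8 allows SAP updates before CDMS freeze or closure, and the SAP change history already records routine corrections in version 2-0. The cost is a brief CRF check and a text edit, with no effect on design, data collection or endpoints.

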# If preceding variable = "Used successfullyyes" then impute missing data with "Used successfully".

Data file, identifier patient display id full & autom SVTYP	Notes	Variable name	Variable label	Variable level	Nominal values
general assessments (see Analysis Set and Data Selection)	case listing for PRPRGB= used, but not successfully OR QSPRGBPR = Yes, with Adverse Event OR QSPRGBPR = Yes, without Adverse Event including programmer serial number DIPRGSNR (see chapter15.1)	COPRGB	NEW: Battery: Please specify reason for unsuccessful use	text	...

Assessment of Programmer Features

Data file, identifier patient display id full & autom SVTYP	Notes	Variable name	Variable label	Variable level	Nominal values
general assessments (see Analysis Set and Data Selection)	descriptive	QSCNSAS	Are the connectivity settings (e.g. WLAN, LAN, printer) easy / difficult to find	nominal	 Very easy  Easy  Adequate  Somewhat difficult  Very difficult
		QSPSAPAS	Are the PSA parameters (e.g. amplitude, basic rate, mode) easy / difficult to find	nominal	 Very easy  Easy  Adequate  Somewhat difficult  Very difficult
		QSPGPV	Is the range of programmable variables for connectivity settings (e.g. WLAN, LAN, printer) sufficient	nominal	 Yes  No
		QSRGPSA	Is the range of the PSA parameters (e.g. amplitude, basic rate, mode) sufficient for the treatment of the patient	nominal	 Yes  No
		QSANYPRB (Note: No missing data need to be imputed)	Did you notice any problems* (including IEGM and ECG recording) which are not mentioned yet relating to the device hardware or software	nominal	 Yes, with Adverse Event  Yes, without Adverse Event  No problem detected

Data file, identifier patient display id full & autom SVTYP	Notes	Variable name	Variable label	Variable level	Nominal values
general assessments (see Analysis Set and Data Selection)	case listing for QSCNSAS = Somewhat difficult OR QSCNSAS = Very difficult including programmer serial number DIPRGSNR (see chapter15.1)	COCNSAS	NEW: Data export: Please specify Somewhat difficult / Very difficult	text	...
	case listing for QSPSAPAS = Somewhat difficult OR QSPSAPAS = Very difficult including programmer serial number DIPRGSNR (see chapter15.1)	COPSAPAS	NEW: Printing: Please specify Somewhat difficult / Very difficult	text	...
	case listing for QSPGPV = No including programmer serial number DIPRGSNR (see chapter15.1)	COPGPV	NEW: Battery: Please specify in case of NO	text	...
	case listing for QSRGPSA = No including programmer serial number DIPRGSNR (see chapter15.1)	CORGPSA	Please specify in case of NO	text	...
	Case listing for all non-missing data including programmer serial number DIPRGSNR (see chapter15.1)	general comment	General comment	text	...

Data file, identifier patient display id full	Notes	Variable name	Variable label	Variable level	Nominal values
data SAR	case listing for any reported problem: QSPGHPRB, QSRFTPRB, QSSAPRB, QSPRPRB, QSPITPRB, QSDFFPRB, QSPRGPRB, QSDFTPRB contain "Yes"; DUPSAAS = No, QSCNNPRB, QSDEXPPR, QSPRNTPR, QSPRGBPR QSANYPRB contain "Yes"	DIPRGSNR (see chapter 15.1)	Programmer serial number	text	...

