### 12.2. Variables

#### Used Programmer Features: Pacing System Analyzer (PSA)

Data file, identifier patient display id full	Notes	Variable name	Variable label	Variable Level	Nominal values
implantation_psa	descriptive	PRIMPASA	Was the PSA functionality used during implantation	nominal	 Yes  No
	descriptive with "not used" handled as missing	QSPLRAS	Polarity selection and documentation	nominal	 used successfully  used, but not successfully  not used
	descriptive#	QSPLRSPR	NEW: Polarity: Did you notice any problem	nominal	 Yes, with Adverse Event  Yes, without Adverse Event  No problem detected
	descriptive with "not used" handled as missing	QSSAAS	Sensing amplitude	nominal	 used successfully  used, but not successfully  not used
	descriptive#	QSSAPRB	NEW: Sensing amplitude: Did you notice any problem	nominal	 Yes, with Adverse Event  Yes, without Adverse Event  No problem detected
	descriptive with "not used" handled as missing	QSPTAS	Pacing threshold	nominal	 used successfully  used, but not successfully  not used
	descriptive#	QSPRPRB	NEW: Pacing threshold: Did you notice any problem	nominal	 Yes, with Adverse Event  Yes, without Adverse Event  No problem detected
	descriptive with "not used" handled as missing	QSPITAS	Impedance test	nominal	 used successfully  used, but not successfully  not used
	descriptive#	QSPITPRB	NEW: Impedance test: Did you notice any problem	nominal	 Yes, with Adverse Event  Yes, without Adverse Event  No problem detected
	descriptive with "not used" handled as missing	QSPNSAS	Phrenic Nerve Stimulation (PNS) test and documentation	nominal	 used successfully  used, but not successfully  not used

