	descriptive#	QSPNSPRB	NEW: PNS test: Did you notice any problem	nominal	 Yes, with Adverse Event  Yes, without Adverse Event  No problem detected
	descriptive with "not used" handled as missing	QSBSAS	Burst stimulation if performed in routine care	nominal	 used successfully  used, but not successfully  not used
	descriptive#	QSBSPRB	NEW: Burst stimulation: Did you notice any problem	nominal	 Yes, with Adverse Event  Yes, without Adverse Event  No problem detected

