### 13.1. Analysis Set and Data Selection

All analyses are performed for patients in the implantation analysis set using a specific data selection before / at implantation.

Data file, identifier	Notes	Variable name	Variable label	Variable level	Nominal values
patient display id full & autom SVTYP					
general assessments	No report	autom SVTYP	Visit type	nominal	
 
○ Implantation
 
○ Pre-hospital discharge follow-up (PHD)
 
○ Regular follow-up after PHD
 

 analysis set imp SAR = Yes  
 Data selection for general assessments with autom SVTYP = implantation

Used Programmer Features: Implant

Data file, identifier patient display id full & autom SVTYP	Notes	Variable name	Variable label	Variable level	Nominal values
general assessments (see Analysis Set and Data Selection)	descriptive	QSPGHAS	Programmer head (PGH) telemetry	nominal	 used successfully  used, but not successfully
	descriptive#	QSPGHPRB	Did you notice any problem* (see definition above) with usage of programmer head telemetry	nominal	 Yes, with Adverse Event  Yes, without Adverse Event  No problem detected
	descriptive with "not used" and "not available..." handled as missing	QSRFTAS	RF telemetry for implant interrogation	nominal	 used successfully  used, but not successfully  not used  not available for implant by default
	descriptive#	QSRFTPRB	Did you notice any problem* (see definition above) with usage of RF telemetry for implant interrogation	nominal	 Yes, with Adverse Event  Yes, without Adverse Event  No problem detected
	descriptive with "not used" handled as missing	QSSAAS	Sensing amplitude	nominal	 used successfully  used, but not successfully  not used
	descriptive#	QSSAPRB	Did you notice any problem* (see definition above) with usage of sensing amplitude	nominal	 Yes, with Adverse Event  Yes, without Adverse Event  No problem detected

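### The SAP 13.1 listing of any reported problem has an incomplete trigger list, a failed implant programming can reach no listing, and no per-use-case count of problems is planned

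*SAP*

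**What the plan says.** The last table under Assessment of Programmer Features in SAP 13.1 defines a listing on the merged file `data SAR`, with the programmer serial number `DIPRGSNR` as its reported variable. The first group of triggers is "case listing for any reported problem: QSPGHPRB, QSRFTPRB, QSSAPRB, QSPRPRB, QSPITPRB, QSDFFPRB, QSPRGPRB, QSDFTPRB contain" the answer Yes. The second is "DUPSAAS = No, QSCNNPRB, QSDEXPPR, QSPRNTPR, QSPRGBPR QSANYPRB contain" the answer Yes. SAP 14.1 repeats chapter 13 for PHD and follow-up.

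SAP 1.2 says that `data SAR` "might be generated by merging all relevant data from the original CDMS data files". It gives no rule for variables that carry the same name in two source files.

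Such names exist. In SAP 12.2 (file `implantation psa`), `QSSAPRB` is labelled "NEW: Sensing amplitude: Did you notice any problem". In SAP 13.1 (file `general assessments`), `QSSAPRB` is labelled "Did you notice any problem* (see definition above) with usage of sensing amplitude". The names `QSPRPRB` and `QSPITPRB` are doubled in the same way.

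SAP 12.2 also has functions with no counterpart in the SAP 13.1 listing, among them "Phrenic Nerve Stimulation (PNS) test and documentation" and "Burst stimulation if performed in routine care", each with its own problem question.

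SAP 10.2 derives `any ade dd SAR` from internally adjudicated ADEs and device deficiencies, and SAP 11.1 repeats it for PHD and follow-up. CIP 7.2.2 makes those events the endpoint. CIP 7.1 names performance and usability among the objectives, and CIP 7.5 lists success of adequate programming among the further data of interest.

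**The concern.** The listing is named as if it gathered every reported problem, and it is the only planned output that joins the CRF problem answers across functions. If its trigger list is short, the report understates which use cases and which programmers had trouble, and nothing in the output shows this.

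CIP 5.3 describes the study as built around use cases, and CIP 11.2 sizes it by use case. The natural performance summary is therefore the number of use cases with at least one problem or unsuccessful function. If the SAP does not define that number, whoever computes it later must choose the definition after seeing the data.

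**Working it through.** The plan states no figure on this point, and the detection probabilities in CIP 11.2 do not depend on it. The check compares variable names and allowed values.

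**Step 1: problem items.** The listing contains 8 + 5 = 13 problem names, plus `DUPSAAS = No`. Compared with every problem question in the SAP:

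| Source | Items | Listed, unique name | Listed, shared name | Not reached |
|---|---|---|---|---|
| PSA (SAP 12.2) | 6 | 0 | 3 | 3: `QSPLRSPR`, `QSPNSPRB`, `QSBSPRB` |
| General assessments (SAP 13.1) | 13 | 9 | 3 | 1: `QSDFPPRB` |
| Accessories (SAP 15.1) | 5 | 0 | 0 | 5: `QSECBPRB`, `QSEDCPR`, `QSPCBPRB`, `QSPADPRB`, `QSACCBPR` |
| Total | 24 | 9 | 6 | 9 |

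The general-assessment gap is a naming error. VectorOpt is defined as `QSDFPPRB`, while the listing writes `QSDFFPRB`, which is defined nowhere in the SAP. `QSECBPRB` matters among the accessory items because it covers the PK-222-L cable, an investigational device.

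The six items under shared names are three names with two sources each. If the names resolve to one source, the listing covers 9 + 3 = 12 of 24 items; if both sources are carried, 9 + 6 = 15 of 24. Reading the misspelt name as intended adds one to either figure.

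**Step 2: success items.** There are 6 (PSA) + 12 (general assessments) + 5 (accessories) = 23 items recording whether a function or accessory was used successfully. None is a trigger. A failed function whose problem question is blank or answered `No problem detected` does not enter this listing.

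**Step 3: are those failures listed elsewhere?** For 22 of the 23 success items, yes: the item's own listing triggers on its unsuccessful value (SAP 12.2, 13.1, 15.1). The connectivity, export and printing listings do not ask for the serial number. The exception is `QSPRGAS`, programming of the implant:

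- Allowed values: `device successfully programmed`, `device not successfully programmed`, `not done`.
- Item listing trigger: `QSPRGAS = used, but not successfully`, or `QSPRGPRB` = Yes with or without adverse event.
- The first condition can never be true, because `QSPRGAS` has no such value.
- Take a case with `device not successfully programmed` and `QSPRGPRB` blank or `No problem detected`. The second condition is false. The imputation note fills a blank only after success, so a blank stays blank.
- The closing listing needs `QSPRGPRB` to contain Yes, which is also false.

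On its programming answers, this case enters no listing. It adds one to the `QSPRGAS` frequency table, without patient ID, serial number or the reason text in `COPRGAS`.

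**Step 4: a count per use case.** No variable in SAP chapters 12 to 16 combines problem and success items. `any ade dd SAR` is Yes only when `AERELSET = Yes` or `DEADED = Yes`, that is, for events adjudicated as relevant to the endpoint. It does not use the CRF problem or success items.

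**The case against.** The strongest defence is that this is simply the closing listing of chapter 13. That chapter selects general-assessment records, its problem items match the trigger list once the misspelling is corrected, and PSA and accessories have chapters 12 and 15. On this reading the omissions follow from scope. That is plausible, and it would settle the shared names in favour of the implant tests. But the SAP does not say so: the table is assigned to `data SAR` and carries an unrestricted label. Even on this reading VectorOpt is misnamed, unsuccessful uses are not triggers, and the programming listing fails.

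The second defence is that single events remain visible in the item listings, and that the SAP 15.1 note on the serial number pairs it with the patient ID, so rows can be traced by hand. This stands for 22 of 23 success items and for every reported problem, including PSA problems. A failed programming might also surface as a device deficiency, which CIP 18.3 defines broadly, or in the general comment. The SAP plans no reconciliation of CRF answers with those records.

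Third, no document promises a rate of problem-free use cases, all analyses are exploratory, and CIP 11.5 sets no pass/fail criteria. This stands and limits the weight of the point.

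A reader might infer several stronger things that the documents do not support:

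- That all PSA problem items are left out. Three PSA names appear, though their source is unclear, and `DUPSAAS = No` is a PSA accuracy answer that is included.
- That this is the only output across functions. `any ade dd SAR` and `n ade dd SAR` also span functions.
- That one of two same-named values is lost in merging. SAP 1.2 describes no merge procedure; what is certain is only that the source is undefined.
- That the plan cannot tell a few troubled use cases from many. The listing is keyed by patient, and Table 3 gives each patient one implantation with its PHD, or one follow-up, so its rows do this for the items it covers.

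**Conclusion.** The point holds as a defect of specification. As written, the listing does not reach 9 of the 24 problem items, leaves the source of three names undefined, and uses none of the 23 success items. One function, programming of the implant, has an item listing that cannot pick up a failure unless a problem is also flagged. No planned output built on the CRF problem and success items counts the use cases with any problem.

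It does not follow that the study is unable to state this count. The items are exported by patient and visit type, so the count can be derived; what is missing is a definition fixed in advance. How many use cases are affected cannot be computed from the documents, because they give no problem rates.

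The conclusion rests on reading variable names and values literally. It concerns the performance objective and further data of interest, not the ADE/DD endpoint, and it leaves sample size unchanged. It should be corrected, but it does not threaten the validity of the study.

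**What to change.** In SAP 12.2 and 13.1, carried through 14.1 and 16.1:

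1. Give the PSA items distinct names in `data SAR` (for example, a PSA prefix on `QSSAPRB`, `QSPRPRB` and `QSPITPRB`), and correct `QSDFFPRB` to `QSDFPPRB`.
2. Change the `QSPRGAS` trigger of its item listing to `device not successfully programmed`.
3. Trigger the closing listing on all PSA, general-assessment and accessory problem items and on every unsuccessful-use value, including `No` for connectivity, export and printing success. Keep `DUPSAAS = No`. Print the triggering item with the patient ID and `DIPRGSNR`.
4. Derive one Yes/No flag per use case for any problem or unsuccessful use, with `not used` and `not done` not counting as unsuccessful. Report n/N for the implantation set and for the PHD/follow-up set as a descriptive performance result, not an endpoint, beside the existing item tables.

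The cost is SAP wording and a few lines of code; no new data are needed. CIP 11.8 allows SAP updates before database freeze or closure. The downside is a longer listing and a summary rate less favourable than any single item rate. The combined flag also pools minor faults, such as printing, with more important ones, which is why the item tables should stay.
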